2.3 Safety Outcomes

Safety will be evaluated by:

- 1. Incidence of device-related, procedure-related and therapy- related adverse events
- 2. Incidence of device-related or unrelated serious adverse events, including unanticipated adverse device effects
- 3. Development of adverse eating behaviors as measured by EDE and QEWP-R

3.0 Study Design

This is a prospective randomized, active treatment controlled, parallel group, multi-center superiority trial of an endoscopically-placed device for weight loss. After the informed consent process, consent forms will be signed and dated, and all subjects who pass the screening process will be randomized in a 2:1 fashion to one of two groups for 52 weeks: AspireAssist plus Lifestyle Therapy ("AT Group") or Control Group (Lifestyle Therapy only). Lifestyle therapy involves treatment with a behavioral education weight loss program delivered as 10 individual or group sessions, in person or by webinar, over 52 weeks. It is, at the site's discretion, whether to provide (i) individual or group sessions or (ii) in-person or by webinar, but a site must provide the same therapy for all subjects. However, in the event, a site that has chosen group sessions are unable to schedule a patient for a group session, the site may provide an individual session for that patient. Aspiration Therapy involves percutaneous endoscopic placement of a gastrostomy device, which permits aspiration of a portion of gastric contents after meals, in addition to lifestyle therapy.

After 52 weeks, Control Group participation will end. The duration of therapy in the Control Group will end at 12 months because the number of drop-outs and rate of weight regain typically increases after 52 weeks of diet and behavioral therapy.

Subjects assigned to the AT Group will have the option to remain in the study for up to 4 more years for follow-up, provided they maintain a minimum of

10% weight loss (from baseline). Since AT requires subjects to perform active therapy and non-responder subjects (e.g., those unable to maintain 10% WL) are not able or do not desire to fulfill this activity, continuing these subjects long-term does not add meaningful data to the study or provide adequate benefit to the subjects. AT subjects who are either non-responders or wish to withdraw from the study will have their A-Tubes removed as soon as can be scheduled and will be followed for 6-months post-tube removal to assess safety and weight maintenance. For those non-responder subjects who have maintained between 5% and 9.9% WL during the study, the option to continue Aspiration Therapy may be considered if the subjects are willing to enroll in the Enhanced Coaching sub-study (provided the study site is participating in this optional sub-study and has received local IRB approval). Since these subjects have already received the A-Tube but have not derived the full benefit of the therapy, it is possible that the additional support and interaction provided in the Enhanced Coaching study may help them become more compliant with AT and improve their weight loss to greater than 10%. Additional information regarding this sub-study is provided in Section 5.5.12.

Safety and efficacy data post-52 weeks will only be summarized for post-market reporting and publications and no statistical hypothesis tested.

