This is a multi-center, randomized, controlled, open-label, 52-week trial to support FDA premarket approval with additional long-term safety and efficacy monitoring of the treatment group for post market reporting and publication purposes. Eligible subjects will be randomized in a 2:1 (treatment: control) ratio to treatment with the Aspiration Therapy (n=117) or lifestyle therapy (behavior education, diet and exercise) program (n=58). The AspireAssist™ Aspiration Therapy System involves percutaneous endoscopic placement of a gastric device that permits aspiration of a portion of stomach contents after meals, in conjunction with lifestyle therapy.

Aspiration Therapy subjects who lose and maintain at least 10% weight loss from baseline will be given the option to continue in the study for an additional four years after the 52-weeks of therapy.

Primary Outcomes:

The first effectiveness primary endpoint is the mean percent excess weight loss (%EWL) at 52-weeks. The hypothesis for the first primary effectiveness endpoint is that the difference in the mean percent excess weight loss (%EWL) at 52-weeks for the Aspiration Therapy (AT) group and Control group is at least 10%. %EWL is defined as absolute weight loss divided by baseline excess weight and multiplied by 100. Excess weight will be determined from ideal body weights based on a BMI=25 kg/m².

The second effectiveness primary endpoint is that at least 50% of the AT group at 52-weeks realizes a %EWL \geq 25%.

Both primary endpoints must be met for the study to be considered a success.

Secondary Outcomes (at 52-weeks)

i) Mean percent absolute weight loss in AT compared to Control group, ii) proportion of subjects who achieve ≥10% absolute weight loss in AT compared to Control group, iii) mean percent change serum lipids (triglyceride, HDL-cholesterol and LDL-cholesterol concentration) in the AT group compared to the control group; iv) mean percent change in systolic and diastolic blood pressures in the AT group compared to the control group; v) "Impact of Weight on Quality of Life" (IWQOL) questionnaire; vi) change in mean hemoglobin A1C (only subjects with T2 diabetes at baseline) , vii) percent procedural success (defined as successful endoscopic placement of the A-Tube) in all subjects undergoing endoscopy; viii) mean percent change in medications

Safety Outcomes:

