5.8 Study Termination

The study ends at 52 weeks. However, AT subjects achieving and maintaining at least a 10% absolute weight loss will be able to continue therapy for an additional 4 years provided subjects maintain ≥10% absolute weight loss (relative to baseline weight), assessed at each annual visit (i.e. years 1, 2, 3, and 4). AT subjects who achieve 5% to 9.9% WL may be considered for continuation of AT therapy after 52 weeks if they enroll in the Enhanced Coaching sub-study.

All study-related expenses, as outlined in the Schedule of Assessments (**Tables 1 - 3**), will be paid for by the Sponsor. Any participant can terminate the study at any time, or the Sponsor can terminate the study for medical reasons. If the participant or Sponsor terminates the study, the implanted A-Tube is removed according to the A-Tube Instructions for Use (IFU) procedures, and all re-usable equipment returned to the Sponsor or destroyed. In addition, the endoscopist may choose to apply an endoclip to enhance fistula closure. Subjects will be followed for 6 months after device explanation (three bi-monthly follow-up visits) to monitor fistula track closure and body weight at 2, 4, and 6 months after explantation. In addition, HbA1C will be checked in subjects with diabetes and those who lost weight and had a reduction in their diabetes medications at the time of A-Tube explantation will need additional glucose monitoring. These subjects will be expected to check their blood glucose concentrations at home at least 2 mornings each week before breakfast for up to 6 months after explantation, and provide this information to the study site every week (by FAX, email, or phone). Specific adjustments in diabetes medications needed to maintain adequate glycemic control will be left to the discretion of the study physician and the subject's primary physician.

Table 4: Schedule of Assessments: Post-Explant			Month		
Month Post-Explant	2	4	6		
Visit window (± weeks)	1	1	1	Total	
Medical & Study Visit (weight, vital signs, concom meds, AE's)	x	x	x	3	
Check fistula track closure	x	x	x	3	
Additional procedures below for subjects with diabetes					
Hemoglobin A1C	x	x	x	3	
Blood glucose monitoring (reported weekly)	x	x	x		
Diabetes medication adjustments, as needed			х		

Upon completion of all study visits, the Study Exit CRF should be completed.

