Buried Bumper. Buried bumper syndrome is a known complication of PEG tubes⁵⁹ that occurs when there is excess tension of the internal bumper against the intragastric wall, which causes migration of the internal bumper into the fistula tract. In the clinical studies to date, there was one such incidence of a buried bumper, which was caused by inappropriate shortening of the A-tube. The clinical team is instructed to determine Skin-Port placement when the subject's abdomen in compressed (seated) to ensure sufficient clearance (~3-10mm) between the Skin-Port and the abdominal wall. Additionally, subjects are instructed to avoid external tension on the Skin Port and to call the physician if the Skin Port feels tight against the abdominal wall.

Persistent Fistula after A-Tube Removal. Although the majority of fistulas close within a few days after tube removal, some subjects will require endoscopic or surgical closure if the fistula does not heal on its own.

Scarring after A-Tube Removal. Removal of the A-tube and fistula closure will result in a scar and skin indentation on the abdominal wall at the ostomy site.

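### Section 3.0 confines post-week-52 safety data to post-market use, while sections 2.3 and 8.4 set no time limit; read literally, most early A-Tube removal harms fall outside the 52-week safety summary

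*Protocol*

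**What the plan says.** **The data boundary.** The Synopsis describes a "52-week trial to support FDA premarket approval with additional long-term safety and efficacy monitoring of the treatment group for post market reporting". Section 3.0 closes with: "Safety and efficacy data post-52 weeks will only be summarized for post-market reporting and publications and no statistical hypothesis tested". Section 5.8 likewise treats week 52 as the end of the study, apart from AT subjects who continue.

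**The removals.** Under section 3.0, AT subjects who are non-responders (unable to maintain 10% weight loss) or who withdraw "will have their A-Tubes removed as soon as can be scheduled and will be followed for 6-months post-tube removal to assess safety". Section 5.8 has the 10% criterion "assessed at each annual visit (i.e. years 1, 2, 3, and 4"), so the first check falls at week 52. There is an exception: "AT subjects who achieve 5% to 9.9% WL may be considered for continuation of AT therapy after 52 weeks", provided they join the optional Enhanced Coaching sub-study. After removal, section 5.8 and Table 4 schedule "three bi-monthly follow-up visits) to monitor fistula track closure and body weight at 2, 4, and 6 months after explantation".

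**The harm.** Section 7.1.2 lists persistent fistula and scarring after tube removal among the device risks and adds that "some subjects will require endoscopic or surgical closure if the fistula does not heal on its own". Section 7.3.1 classes the risks of section 7.1.2 as device-related adverse events.

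**The safety outcome.** Section 2.3 makes the incidence of device-related adverse events a safety outcome. Its heading has no 52-week label, although the headings of 2.1 and 2.2 do. Section 8.4 tabulates adverse events with no time limit.

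**The concern.** Harm from removing the tube can arise only after removal. The protocol names that harm, triggers a group of removals at the week-52 check and schedules visits to look for it. The last sentence of section 3.0 then sends everything after week 52 to post-market reports and publications, for safety as well as efficacy. Sections 2.3 and 8.4 point the other way, so two analysts following the same protocol could produce different device-related event tables.

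What is at stake is how well the premarket safety summary can describe a listed device risk. If section 3.0 governs, that description rests on subjects removed before week 52, and only on the part of their six-month follow-up that falls before week 52.

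**Working it through.** **Inputs from the protocol**
- AT group 117 of 175 (8.1.1); AT drop-out 10% (8.1.2).
- Expected share of AT subjects reaching 25% excess weight loss (EWL) 66%; SD of EWL 20% (8.1.1).
- Ideal weight at BMI 25 (2.1); AT feasibility BMI 42.6, SD 4.7 (section 1.3, Feasibility Trial); eligible BMI 35 to 55 (4.1).

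**Assumptions, not in the protocol**
- Every drop-out has a documented tube removal, and exits are spread evenly over the year.
- EWL is normally distributed and independent of BMI.
- Persistent-fistula risk of 1% to 10%.

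**Step 1. Reproduce the plan's figure.** For 66% against 50%, significance level 0.025 and power 90%:
n = [(1.960 × √(0.5 × 0.5) + 1.282 × √(0.66 × 0.34)) / 0.16]² = 98.4, rounded up to 99. This matches section 8.5.2. Two thirds of 175 is 117.

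**Step 2. Removals before week 52.** 117 × 0.10 = 11.7, about 12. With even exits, those at least 2 months past removal by week 52 number 12 × 10/12 = 10, and those at least 6 months past number 12 × 6/12 = 6. Drop-out of 5% to 20% gives about 6 to 23 removals.

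**Step 3. Subjects below the weight threshold at week 52.**
- Mean EWL = 25 + 20 × z(0.66) = 25 + 20 × 0.412 = 33.25%.
- Percent weight loss = EWL × (BMI − 25) / BMI. At BMI 42.6, 10% weight loss is 24.2% EWL and 5% is 12.1% EWL.
- P(loss < 10%) = Φ((24.2 − 33.25)/20) = 32.6%. P(loss < 5%) = Φ((12.1 − 33.25)/20) = 14.5%.
- Averaged over BMI with mean 42.6 and SD 4.7, truncated to 35 to 55, these become 33.5% and 14.8%.
- Completers: 117 − 12 = 105. Below 10%: 105 × 0.335 = 35. Below 5%: 105 × 0.148 = 16.

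So about 35 removals follow the week-52 check if nobody uses the 5 to 9.9% exception, and about 16 if everyone eligible does. Setting the model aside and assuming 20% to 50% below the threshold gives about 21 to 53, before any use of the exception.

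**Step 4. What each denominator can show.** The explanted group is 12 under section 3.0 read literally. It is 12 + 16 = 28 to 12 + 35 = 47 if week-52 removals count. P(at least one case) = 1 − (1 − p)ⁿ:

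| Assumed risk p | n = 12 | n = 28 | n = 47 |
|---|---|---|---|
| 1% | 11% | 24% | 38% |
| 2% | 22% | 43% | 61% |
| 5% | 46% | 76% | 91% |
| 10% | 72% | 95% | 99% |

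A measure that needs no assumed risk is the one-sided 95% upper bound when no case is seen, 1 − 0.05^(1/n). It is 22% for n = 12, 10% for n = 28 and 6% for n = 47.

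**The case against.** The strongest defence is that the last sentence of 3.0 follows the description of the optional extension and ends by ruling out hypothesis tests. It may have been meant only to say that extension data are descriptive. Sections 2.3 and 8.4 carry no week-52 limit, section 7.3.1 requires serious events to be reported with no such cut-off, and section 7.3.2 follows treatment-emergent events to resolution or a stable end-point. The visits exist, no safety hypothesis depends on the outcome, and a separate statistical analysis plan, not available here, may set the window.

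Much of this stands. It rules out several stronger readings that a reader might infer:
- *Removal harms are deliberately or definitively excluded.* The documents do not settle this, because their sections disagree.
- *Nobody follows these subjects.* Table 4 and the reporting rules show otherwise.
- *All AT subjects are explanted at week 52.* Removal there applies to those below 10% loss, with the 5 to 9.9% exception.
- *The early removals are simply subjects who quit.* Removals also follow adverse events, pregnancy or termination by the sponsor, and some drop-outs may be lost before a documented removal. The count of 12 is a proxy that could err either way.
- *Only the 6 with a completed month-6 check are informative.* Section 7.1.2 expects most fistulas to close within days, so the 10 or so who reach month 2 are informative too.
- *Device-related incidence is understated.* A rate to week 52 is a valid time-bounded figure; it is incomplete for removal harms.

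The defence does not remove the wording itself. The sentence in 3.0 covers safety as well as efficacy, says such data are used only for post-market purposes, and has no exemption for post-explant follow-up.

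**Conclusion.** The point holds as a conflict between section 3.0 and sections 2.3 and 8.4 that must be reconciled. If 3.0 is followed literally, a named device risk is described in the 52-week summary from about 12 removals with truncated follow-up, instead of roughly 28 to 47.

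The 12 rests on the plan's 10% drop-out. The 16 to 35 week-52 removals are model-based and depend on the plan's 66% and SD of 20%, the feasibility BMI and use of the sub-study exception. The detection probabilities depend heavily on the assumed fistula risk, for which the protocol gives no value, so they should be read as a range. The primary endpoints, conduct of the trial and protection of subjects are unaffected.

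**What to change.** Amend the last sentence of section 3.0 and align 2.3 and 8.4 with it. State that the main safety summary includes adverse events through the existing Table 4 post-explant visits for every AT subject whose A-Tube is removed before, at or because of the week-52 assessment. Tabulate removal-related events (persistent fistula, closure procedures) with explanted subjects as the denominator. If the database is locked before that follow-up is complete, report what is available and send the rest as a safety update. Extension data from continuing subjects can stay descriptive and post-market.

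The cost is protocol and analysis-plan wording plus one table. These rows mature up to about 6 months after week 52, and the event rates may look slightly less favourable. No change to visits or to any removal rule is proposed.

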4.0 Study Population & Recruitment

The study population is 175 obese men and women who (i) have a Body Mass Index (BMI) between 35.0 and 55.0 kg/m², (ii) are 21-65 years old, and (iii) have failed to achieve and maintain weight loss with non-surgical weight loss therapy.

Subjects will be enrolled at 8-12 sites within the United States. Each site is encouraged to enroll, on average 15 subjects (i.e. 10 treatment group and 5 control group) and no fewer than 10 subjects. No site may enroll more than (30) subjects.

Randomization will be stratified for both initial BMI and sex to help ensure equal number of males in both the therapy and control group and to guarantee that extremely obese subjects (BMI >40 kg/m²) are equally distributed between the study groups. Initial BMI, sex, and race will be compared between study groups and adjusted in the analysis as covariates if an imbalance is found between groups.

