5.2 Randomization

Eligible subjects who fulfill all enrollment criteria obtained during Screening will be randomized to the Treatment or Control Group in a 2:1 ratio, stratified by sex and BMI (< or ≥ 40.0 kg/m2) at each study site. A web-based randomization scheme will be established to ensure there is no possibility that group assignment can be known in advance. To avoid temporal bias, randomized blocks of varying sizes will be used to prevent investigators from having advanced knowledge of the assignment of the last subject in a given block. Randomization will occur within 14 days of the screening visit. Subjects will be notified by telephone of their group assignment.

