8.2 Statistical Methods

Tabulation of summary statistics, graphical presentations, and statistical analyses will be performed using SAS® software. Where not otherwise specified, the last pre-treatment (i.e. for treatment group, this is prior to the initiation of therapy) observation will be used as baseline for calculating post-treatment changes from baseline. The primary presentations and analyses will be based on data pooled across study centers. Relevant summaries for individual centers, or combinations of centers, may be presented for primary data. All testing and confidence intervals will use a significance level of 5%.

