8.5 Statistical Analysis Plan

All safety and efficacy analyses will be conducted on the intent-to-treat (ITT) population, defined as all subjects who undergo treatment in either the AT or Control group. Primary effectiveness analyses be performed without imputation; that is the "ITT evaluable" dataset will include only the observed data from each study visit. Imputation of missing values (e.g., using the methodologies outlined above) will be performed for subjects who terminate prematurely or are lost to follow-up. Those dropout subjects that have device-related adverse events, or other obvious reasons that lead to negative outcomes, will be imputed as failures in the primary analysis. As a sensitivity analysis the primary effectiveness endpoint will be re-analyzed using only data from completers.

A poolability analysis and covariate analysis will be performed. The demographic characteristics as well as the two primary endpoints will be examined for poolability across sites. The impact of important covariates will be examined for the two primary efficacy endpoints. These covariates will include race, age, gender, and initial BMI.

An internal, 6-month analysis will be performed on all endpoints to ensure systematic data collection at all sites and to identify potential safety concerns. The results of this analysis will not affect the clinical investigation plan unless a previously unidentified risk to study participants is discovered.

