8.5.1 Sample Size for Primary Endpoint #1 (Hypothesis One)

Primary endpoint #1: The observed difference in the mean excess weight loss (%EWL) at 52-weeks for the AT group and control group is > 25%. %EWL is defined as absolute weight loss divided by baseline excess weight and multiplied by 100. Excess weight will be determined from ideal body weights based on a BMI=25 kg/m2.

The first hypothesis presented is

 H_0 : $\mu_F - \mu_S < \delta$ versus H_A : $\mu_F - \mu_S \ge \delta$

Where μ_F is the observed %EWL for the **AT Group** and μ_S is the observed %EWL for **Control Group**. The value of δ is the clinically significant threshold value. Statistical differences between AT and Control groups will be evaluated by using a two-sample t-test. Using this hypothesis and the two-sample t-test, **Table 8.5.1** presents the sample size for the AT group (total in parenthesis) assuming a 2:1 randomization with the assumptions listed in the table. The significance level is 0.025 and the power = 90%.

Table 8.5.1 Requisite Sample Size for a 90% Power

			Observed Difference in Mean %EWL between AT and			
			Control			
Power	δ	Std.Dev	15%	20%	25%	30%
90%	10	15	286 (429)	74 (111)	34 (51)	20 (30)
		20	506 (759)	128 (192)	58 (87)	34 (51)
		25	790 (1185)	200 (300)	90 (135)	52 (78)
90%	15	15	Na	286 (429)	74 (111)	34 (51)
		20	Na	506 (759)	128 (192)	58 (87)
		25	Na	790 (1185)	200 (300)	90 (135)

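### Randomisation is stratified by sex, BMI and site, but endpoint #1 uses an unadjusted t-test, with covariates added only under an undefined imbalance rule that omits site

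*Protocol*

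**What the plan says.** - **Allocation.** Protocol 5.2 randomises 2:1, "stratified by sex and BMI (< or ≥ 40.0 kg/m2) at each study site". Section 4.0 names only two of these factors: "Randomization will be stratified for both initial BMI and sex".
- **Primary test.** Section 8.5.1, for endpoint #1: "Statistical differences between AT and Control groups will be evaluated by using a two-sample t-test". The margin is 10 %EWL and the significance level 0.025.
- **Site.** Section 8.2: "The primary presentations and analyses will be based on data pooled across study centers".
- **Adjustment rule.** Under section 4.0, the arms are compared on initial BMI, sex and race, and these are "adjusted in the analysis as covariates if an imbalance is found between groups". It gives no test, cut-off or model form.
- **Further covariate work.** Section 8.5 plans poolability across sites and a covariate analysis covering race, age, gender and initial BMI: "The impact of important covariates will be examined for the two primary efficacy endpoints". This carries no imbalance condition, but it is not named as the primary test.
- **Baseline comparison.** Section 8.3 plans homogeneity tests between arms and does not link them to the adjustment rule.

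**The concern.** The design balances the arms on sex, BMI and site, and the primary test then ignores all three. When those factors predict outcome, balancing them removes some chance variation from the between-arm difference. The t-test's standard error does not reflect that, so it comes out too large.

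The adjustment rule does not repair this. Stratification makes imbalance in sex and BMI unlikely, so adjustment would rarely be triggered for them. Site is not on the list, although section 3.0 lets each site choose individual or group, in-person or webinar lifestyle sessions, so a site effect is plausible. With no threshold, two analysts could follow section 4.0 and fit different models to the same open-label data. Endpoint #1 is one of two endpoints that must both be met.

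BMI also enters the endpoint by construction. Excess weight is measured from BMI 25, so a given percentage weight loss converts to a different %EWL at each baseline BMI.

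**Working it through.** **1. The plan's own figure.** Inputs from sections 8.1.1 and 8.5.1: difference 25, margin 10, SD 20, 2:1 allocation, 90% power, 0.025 taken as one-sided.

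n(control) = (1 + 1/2) × (1.960 + 1.282)² × 20² / (25 − 10)² = 28.02, rounded up to 29. AT = 58, total = 87.

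This matches Table 8.5.1, and the noncentral-t power at 29/58 is 90.3%. The formula has no covariate or stratum term, so the planning is unadjusted as well.

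**2. Power at the enrolled size.** SE = 20 × √(1/117 + 1/58) = 3.21. Power = Φ(15/3.21 − 1.96) = 99.7%. With observed cases only, at the drop-out rates in section 8.1.2 (117 × 0.9 ≈ 105; 58 × 0.8 ≈ 46), SE = 3.54 and power is about 98.9%.

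**3. What adjustment could gain.** The protocol gives no R-squared, so a range is assumed. Adjusted SE = 3.21 × √(1 − R²).

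| Assumed R² | 0 | 0.05 | 0.10 | 0.20 | 0.30 |
|---|---|---|---|---|---|
| SE at 117/58 | 3.21 | 3.13 | 3.05 | 2.87 | 2.69 |
| Total N for 90% power | 87 | 81 | 78 | 69 | 60 |
| Power, true excess over margin 8 | 70% | 72% | 75% | 80% | 85% |

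At the planned excess of 15, power is 99.7% unadjusted and at least 99.8% for each adjusted case.

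**4. Behaviour under stratified allocation.** Null simulation, 12,000 runs per row: N = 175, 10 sites, permuted blocks within site × sex × BMI, SD 20. The factor effects are assumed, the prognostic score and adjusted model also include race, and the imbalance trigger is assumed to be baseline p < 0.05.

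| R² | t-test reported SE | t-test sampling SE | Adjusted sampling SE | Triggered sampling SE | Type I error: t-test / adjusted / triggered |
|---|---|---|---|---|---|
| 0 | 3.21 | 3.21 | 3.24 | 3.21 | 2.6 / 2.6 / 2.6% |
| 0.1 | 3.21 | 3.14 | 3.06 | 3.13 | 2.3 / 2.6 / 2.3% |
| 0.2 | 3.21 | 3.08 | 2.91 | 3.05 | 2.0 / 2.4 / 1.9% |
| 0.3 | 3.21 | 2.97 | 2.71 | 2.95 | 1.7 / 2.4 / 1.7% |

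The t-test's reported SE does not move as R² rises, although its true sampling SE falls. The trigger changed the model in about 5% of trials and recovered almost no precision.

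**5. BMI alone.** From the endpoint definition, %EWL = % weight loss × BMI/(BMI − 25). A 10% weight loss is 35% EWL at BMI 35, 27% at BMI 40, 24% at BMI 42.6 and 18% at BMI 55.

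Assume weight loss independent of BMI; BMI mean 42, SD 5, truncated to 35-55; AT weight loss 12% (SD 7), 15% (SD 8) or 18.6% (SD 7.3); Control 4-6% (SD 6-7). BMI then explains about 5-11% of %EWL variance in AT and about 1-2% in Control. With allocation stratified at BMI 40, adding continuous BMI with a common slope lowered the reported SE of the difference by 1.7-3.6%. The true sampling SE changed by less than 0.5%. From BMI alone, the gain is therefore in the reported SE, with almost none in the precision of the estimate.

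**The case against.** The strongest reply is that nothing here is invalid. Section 8.5.1 names one test, and an unadjusted t-test after stratified allocation errs on the safe side. The section 4.0 trigger looks at baseline characteristics and not at outcomes. Section 8.5 already examines covariates and site poolability unconditionally, and model detail can be left to a SAP. Endpoint #2 sets the sample size and, as a single-arm proportion, is untouched by an ANCOVA of endpoint #1.

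Most of this stands, and it rules out several stronger readings that a reader might infer:

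- **That endpoint #1 is underpowered.** Power is about 99.7% under the protocol's own assumptions. Lost precision matters only if the true difference is well below plan or the SD well above it.
- **That conditional adjustment inflates type I error.** The simulated trigger stayed at or below the nominal 2.5%, within simulation error.
- **That the protocol considers covariates only after an imbalance.** Section 8.5 plans to examine them in any case.
- **That the AT-arm R-squared gives the gain in the test.** An R² of 5-11% would narrow the error within that arm by about 3-6%. With equal SDs, Control contributes (1/58)/(1/58 + 1/117) = 67% of the variance of the difference, and BMI explains little there.
- **That the t-test always overstates the SE.** It does so only if the factors are prognostic.

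The reply does not remove the central point. Section 4.0 states an analysis rule rather than deferring one, and the rule is undefined. It does not say whether an adjusted result would replace the t-test or sit beside it. Section 8.5 does not settle that, and its list includes age, which section 4.0 omits.

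**Conclusion.** The point holds as a weakness in a stated method. The primary test of endpoint #1 ignores the randomisation factors, and the rule for bringing some of them back is undefined, omits site and would seldom be triggered for sex or BMI.

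The consequence is a conservative test whenever those factors are prognostic. The size rests on assumptions: about 2-3% of the reported SE from BMI alone under the model in step 5, more if sex or site predict outcome, and nothing at R² = 0. Neither planned power nor type I error is at risk. The change is worth making because it removes an open choice in one of the two analyses that decide whether the trial succeeds.

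**What to change.** - Prespecify the primary analysis of endpoint #1 as an ANCOVA of week-52 %EWL on arm, continuous baseline BMI, sex and site, fitted regardless of observed balance, with the adjusted difference tested against 10. Fix in advance how small sites are pooled.
- Delete the imbalance condition from section 4.0.
- Keep the unadjusted two-sample t-test as a supportive analysis.
- Reconcile the covariate lists in sections 4.0 and 8.5, and state the role of each analysis. Name site as a stratification factor in section 4.0, to agree with section 5.2.

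The cost is wording in the protocol and SAP, since BMI, sex and site are already collected. If none of the factors is prognostic, the adjusted SE is about 1% larger (3.24 against 3.21 in the simulation), which is negligible at this sample size.
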